19.4. Audits

The study may be subject to a quality assurance audit by InnFocus or its designees, as well as inspection by appropriate regulatory authorities. It is important that the Investigator and relevant study staff are available during on-site monitoring visits or audits and that sufficient time is devoted to the process.

This study may be selected for audit by quality assurance representatives from InnFocus or an authorized designee. Inspection of site facilities (e.g., investigational device storage, laboratories) and

review of study-related records will occur during such audits in order to evaluate the trial conduct and compliance with the CIP, ISO 14155:2011, GCP and applicable local regulatory requirements.

20. Data Management

A separate Data Management Plan (DMP) will govern all aspects of data management including the creation of CRFs and other electronic data capture methods; database design; data security; data retention and backup/recovery plan; process for data entry into the CRF/EDC; the data validation process including query management; database audit plan, and database acceptance criteria.

All documents and data shall be produced and maintained in a way that assures control and traceability. All documents and subsequent versions related to the clinical study shall be identifiable, traceable, and appropriately stored to provide a complete history of the clinical investigation. The Principal Investigator shall ensure accuracy, completeness, legibility, and timeliness of the data reported to InnFocus on the eCRF and in all other reports required by this CIP. The data recorded on the eCRF shall be derived from source documents and any discrepancies shall be explained in writing. The eCRF shall be electronically signed by the Principal Investigator or authorized designee. Any change or correction to source data reported on a CRF shall be dated, initialed or explained if necessary, and shall not obscure the original entry.

20.1. Recording Data

The study data will be recorded on electronic case report forms (eCRF). Source documents, and any worksheets used as source documents, will be filed in the subject's medical record. Office visit data will be recorded by the Investigator, or a designated representative.

A Regulatory Binder (Investigator Site File) will be provided to store all study documents and forms. All of the data will be properly recorded in standard hospital charts and forms as well as in the eCRFs. The data will include the examination and evaluation methods described in this protocol such as:

- Results of study procedures
- Subject imaging photos
- Adverse event reporting (if applicable)
- Deviation reporting (if applicable)
- Reoperations (if applicable)

Consented subjects will be entered on the subject Screening and Enrollment Log. Consented subjects who are deemed eligible for participation in the study based on the enrollment process will continue to use the subject identification numbers assigned during the INN-005 study, in order to track individual subject data.

20.2. Data Handling and Record Keeping

20.2.1. Subject Identification

Subjects will be identified by a five (5) digit Subject ID number composed of a one-digit study identification number, a two-digit center identification number, followed by a two-digit sequential subject number. The subject ID will be the same number given when the subject originally enrolled under the INN-005 study. Subject initials may also be included on eCRFs, in accordance with local regulations.

20.2.2. Subject Accountability

All subjects enrolled in this clinical study shall be monitored for the duration of the investigation. The clinical study shall be considered completed when all subjects that have been enrolled in the investigation, including subjects whose device was removed or replaced, have completed the Month 60 Follow-Up Visit.

20.2.3. Confidentiality

All medical records associated with the clinical study will be made available for review by InnFocus personnel, its Contract Research Organization (CRO), and any governmental/regulatory agencies involved. The results of the study may be published in the future for scientific and marketing purposes, but the identity (name) of each subject will not be revealed. All records will be stored in a secure area at the Investigator's facility, the CRO, and at InnFocus, Inc.

20.2.4. Source Data and Electronic Case Report Forms

All investigative sites will be given instructions by a trained InnFocus designee on case report form completion at the site initiation visit and/or interim monitoring visits. Source documents are to be maintained at the site in the Subject Binder. All entries must be made in black or blue ink and changes must be made by strike-through only with date and initials or signature. All source worksheets, used as source documents, must be completed and signed and dated by either the Principal Investigator or the site staff member conducting the assessment. No correction fluid or correction tape is to be used on the source documents. The source document will be used by the Sponsor to verify data submitted on the eCRFs. The source document data will be entered into a validated Electronic Data Capture (EDC) system at each site by trained study staff in accordance with 21CFR Part 11 requirements.

20.3. Data Management

The study database will be designed to be compliant with 21 CFR Part 11 and relevant guidance documents. The electronic database will be developed and maintained by an independent Contract Research Organization (CRO), Promedica International Inc.

The database will incorporate time-stamped audit trails, protection of human subjects, restricted access, and data security at the component level. Each database module, including each individual eCRF, will be validated by conducting a series of standard tests that demonstrate usability and correctness of the database system. The database will be maintained on an ongoing basis and will be routinely backed up with both onsite and offsite storage.

21. Statistical Analysis and Methods

This is a concurrent controlled, open-label, long-term follow-up study of the safety of the PRESERFLO® MicroShunt device. All inferential statistics will be provided at the 5% nominal significant level. Data generated in this study may be continuous with data generated in the INN-005 study. The primary analysis of the INN-005 protocol has already been conducted and additional labeling claims are not intended to be made from analyses performed for this Extension study. Detailed analyses will be provided in the Statistical Analysis Plan (SAP).

21.1. Sample Size Considerations

All 629 subjects who were randomized into both Phase I and II of the INN-005 study, and have completed their Month 24 Follow-Up Visit, will be assessed for eligibility to participate in this long-term follow-up study. The sample size will therefore be dependent upon the number of subjects who are willing to participate in, and who meet the eligibility criteria for, this study.

21.2. Safety Outcome Measures

This long-term safety study does not specify any hypotheses to evaluate the study outcome measures. Descriptive statistics will be used to summarize safety, effectiveness, and ancillary data. The Primary Safety Outcome Measure is incidence of sight-threatening adverse events, as defined in sections 12 and 13.3.

21.3. Effectiveness Outcome Measures

Evaluating long-term effectiveness is a secondary outcome measure of the study. The main effectiveness outcome measure is the overall success rate, which is defined as the proportion of study eyes with $\geq 20\%$ decrease in intraocular pressure from INN-005 study screening to 60 months of post-operative follow-up without increasing the number of glaucoma medications. This proportion, along with the 95% confidence interval will be summarized for the treatment group and the control group. Further details will be provided in the SAP.

Analyses of effectiveness outcomes will consider subjects that fall into a failure category. Failure is defined as a subject with one or more of the following:

- 1. No light perception vision confirmed on two consecutive follow-up visits
- 2. IOP persistently below 6mmHg (defined as an intraocular pressure below 6mm that is present on two consecutive study follow-up visits)
- Requiring a reoperation in the study eye, performed in an operating room, consisting of the following:
 - a) Trabeculectomy
 - b) Placement of a drainage device
 - c) Bleb revision (other than needling)
 - d) Explantation or repositioning of the PRESERFLO® MicroShunt
 - e) Iridectomy
 - f) Resuturing of the scleral flap
 - g) Glaucoma laser procedure (e.g. trabeculoplasty, iridotomy)

- h) Other glaucoma surgery to reduce IOP
- i) Introduction of an oral carbonic anhydrase inhibitor

The procedures below will be reported as complications but will not be considered failures:

- 1. Needling of the bleb with or without the use of an injected antifibrotic
- Laser removal of the blockage at the tip of the PRESERFLO® MicroShunt or at the Anterior Chamber entry point for a trabeculectomy
- 3. Use of a viscoelastic to limit aqueous flow

The following procedures will not be considered as failures or complications but will be documented:

- Eye massage
- 2. Laser suture lysis in a trabeculectomy

Other effectiveness outcome measures will include the following:

- Mean change in IOP from INN-005 study screening.
- Proportion of study eyes with any qualifying glaucoma-related post-operative intervention.
- Proportion of study eyes considered a treatment success (complete, qualified). Complete
 success is defined as patients with 20% reduction in IOP from Screening, without glaucoma
 medication supplement. Qualified success is defined as patients with 20% reduction in IOP from
 Screening with glaucoma medication supplement.
- Change in the number of glaucoma medications from INN-005 study screening.
- For categorical endpoints, frequencies and percentages will be used. For continuous endpoints, mean, median, standard deviation, minimum, and maximum will be used. As previously stated, no labeling claims will be made from these analyses.

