8.1.4.2. Physical Interventions

8.1.4.2.1. Glaucoma Reoperations

Secondary surgical procedures which will be considered as failures of the INN-005 study original procedure include:

- 1. Trabeculectomy
- 2. Placement of a drainage device
- 3. Bleb revision (other than needling)
- 4. Explantation or repositioning of the PRESERFLO® MicroShunt
- 5. Iridectomy
- 6. Resuturing of the scleral flap
- 7. Glaucoma laser procedure (e.g., trabeculoplasty, iridotomy)
- 8. Other glaucoma surgery to reduce IOP

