8.1.5. Treatment Success and Failure

Total treatment success is defined as a subject with 20% or more reduction in IOP from the INN-005 study Screening to 60 months of post-operative follow-up without increasing the number of glaucoma medications.

Complete treatment success is defined as a subject with 20% or more reduction in IOP from the INN-005 study Screening without any glaucoma medication.

Qualified treatment success is defined as a subject with 20% or more reduction in IOP from the INN-005 study Screening with glaucoma medication supplement. The number of glaucoma medications should not exceed that at the INN-005 study Screening.

For this study, a *failure* is defined as a subject with one or more of the following:

- 1. No light perception vision confirmed on two consecutive study follow-up visits (i.e., two consecutive annual scheduled visits).
- 2. IOP persistently below 6mmHg (defined as an intraocular pressure below 6mm that is present on two consecutive scheduled/unscheduled visits).
- 3. Glaucoma Reoperations listed in Section 8.1.4.2.1.
- 4. Introduction of an oral carbonic anhydrase inhibitor.

The glaucoma needling procedures, listed in Section 8.1.4.2.2, and use of a viscoelastic to limit aqueous flow will be reported as *complications* but will not be considered failures, while other procedures, listed in Section 8.1.4.2.3, will not be considered as failures or complications.

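### The failure definition behind the 60-month total success rate is inconsistent within the protocol, between protocol and SAP, and through a wrong cross-reference in the SAP

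*Protocol*

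**What the plan says.** Protocol 21.3 states: "The main effectiveness outcome measure is the overall success rate". This is an IOP reduction of at least 20% from INN-005 screening to 60 months with no more glaucoma medications than at screening. The section then lists the failure categories that effectiveness analyses are to consider.

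- **Reoperation.** Protocol 21.3 item 3 reads "Requiring a reoperation in the study eye, performed in an operating room, consisting of the following". Its sub-items include glaucoma laser and, as the last one, starting an oral carbonic anhydrase inhibitor (CAI). SAP 8.1.5 instead counts every procedure in SAP 8.1.4.2.1, including "Glaucoma laser procedure (e.g., trabeculoplasty, iridotomy)", without regard to setting, and makes oral CAI a separate item.
- **Hypotony.** Protocol 21.3 has "defined as an intraocular pressure below 6mm that is present on two consecutive study follow-up visits". SAP 8.1.5 has "defined as an intraocular pressure below 6mm that is present on two consecutive scheduled/unscheduled visits".
- **Other protocol text.** Section 11.1 treats a secondary procedure, including glaucoma laser other than for blockage removal, as failure of the original procedure. Section 11.2 counts a required oral CAI as failure. Neither mentions an operating room. The needling text in 11.1 refers to 21.3 for what failure means.
- **Use in the analysis.** SAP 8.3.1 makes subjects with failure events by 60 months non-responders, and SAP 8.3 censors IOP after such events. Both cite SAP 8.1.4.3 for the definition of failure. SAP 8.1.4.3 defines qualifying glaucoma-related interventions; failure is defined in SAP 8.1.5.

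**The concern.** SAP 8.3.1 reports the success rate in each group, the difference and 95% confidence intervals, in both the Enrolled and Per-Protocol populations. The responder flag has to be programmed from a single rule, and here a programmer finds several. An office laser procedure, a short spell of hypotony or a needling can make the same eye a success or a failure, depending on which section is read.

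The cross-reference is the most serious part, because it lies in the section that specifies the analysis. The protocol conflict matters for a different reason: a reader of the study report who checks the success rate against Protocol 21.3 would find a different definition and no explanation.

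**Working it through.** The documents give no expected success rate, failure rate or sample size calculation, so there is no planned figure to reproduce. The check is a comparison of texts, followed by the arithmetic of how a reclassified eye moves the rate.

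**Step 1. The same event under each text**

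| Event in the study eye | Protocol 21.3 | Protocol 11.1 / 11.2 | SAP 8.1.5 | SAP 8.1.4.3, as cited for failure |
|---|---|---|---|---|
| Laser trabeculoplasty outside an operating room | Not a failure | Failure | Failure | Listed |
| Oral CAI started | Only as a sub-item of operating-room reoperation | Failure | Failure | Listed (any medication) |
| Topical medication restarted, count not above screening | Not a failure | Not called a failure | Not a failure | Listed |
| Needling | Complication, not failure | Not a failure | Complication, not failure | Listed |
| Viscoelastic to limit flow | Complication, not failure | Not called a failure | Complication, not failure | Listed |
| Laser suture lysis | Neither | Routine practice | Neither | Listed |
| IOP below 6 mmHg on two close unscheduled visits only | Not a failure | – | Failure | Not listed |
| IOP below 6 mmHg at Months 36 and 48, 6 or more at an unscheduled visit between | Failure | – | Not a failure | Not listed |
| Confirmed loss of light perception | Failure | – | Failure | Not listed |

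**Step 2. The cross-reference.** Taken literally, SAP 8.1.4.3 errs in both directions. It adds four kinds of event that SAP 8.1.5 does not count: needling, viscoelastic use, suture lysis and topical medication. It omits two that SAP 8.1.5 does count: hypotony and loss of light perception. Counting any introduced medication as failure also conflicts with total success itself, which allows medication up to the screening number. Suture lysis is listed only for trabeculectomy, so that entry could affect only the control group.

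**Step 3. The hypotony wording is a real difference.** In the same SAP list, item 1 reads "No light perception vision confirmed on two consecutive study follow-up visits (i.e., two consecutive annual scheduled visits)". The SAP therefore uses the protocol's phrase to mean annual visits, and chooses other words for hypotony. Protocol 9.6.4 also treats unscheduled visits as a separate kind. Scheduled visits fall at Days 1080, 1440 and 1800, each ± 90:

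- nominal gap: 1440 − 1080 = 360 days
- shortest gap: (1440 − 90) − (1080 + 90) = 180 days
- longest gap: (1440 + 90) − (1080 − 90) = 540 days

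Two unscheduled visits can be much closer. The hypotony rows in the table show that neither rule contains the other.

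**Step 4. When the rule decides the result.** An IOP below 6 mmHg is a reduction of at least 20% whenever screening IOP is at least 6 / 0.8 = 7.5 mmHg. For such an eye with no added medication and no other failure event, the hypotony rule alone separates success from failure.

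**Step 5. Effect on the rate.** Let m of n eyes meet the IOP and medication criteria, and let f be the number of those m that the failure rule removes. Success is (m − f)/n, so two rules differ by (f₁ − f₂)/n. An eye that already misses the IOP or medication criterion does not move the rate.

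For illustration only, assume n = 100 per group and 60% success (50.4 to 69.6). The Wald interval is p ± 1.96√(p(1 − p)/n).

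- 2% reclassified: 58% (48.3 to 67.7)
- 5% reclassified: 55% (45.2 to 64.8)
- 10% reclassified: 50% (40.2 to 59.8)

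For the group difference, assume 55% against 60%, which is −5 points (−18.7 to 8.7). Reclassifying 5% and 0% gives 50 − 60 = −10 (−23.7 to 3.7). Reclassifying 2% and 5% gives 53 − 55 = −2 (−15.8 to 11.8). The direction depends on which group has more affected eyes, and the documents do not say.

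**The case against.** The strongest reply is that the working rule is already settled. Protocol 21 and 21.3 leave analysis detail to the SAP, and SAP 1 makes the approved SAP the basis of the study report. SAP 8.1.5 sets the visit type separately for light perception and for hypotony, which looks deliberate. Most of this stands: a reader might infer that the reported rate is open to a choice between two documents, but SAP 8.1.5 is the natural source. What remains is that the SAP does not flag its departure from Protocol 21.3, and that its own analysis sections cite the wrong section.

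A reader might also infer that under the protocol an oral CAI can never count as failure, or that office laser never does. Protocol 11.1 and 11.2 count both with no setting condition, so the fault is a conflict inside the protocol. For oral CAI it is a nesting slip with little practical effect.

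Nor do the documents show that the SAP hypotony rule always finds more failures as visits increase. An unscheduled reading of 6 mmHg or more between two low annual readings breaks the run and removes a failure. What holds is that the rule depends on discretionary visits in an open-label study.

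Finally, the outcome is secondary, with no hypothesis, no labeling claim and exploratory intervals. That is correct and limits the weight of the point.

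**Conclusion.** The point holds as an inconsistency in the failure definition, with three parts: the operating-room condition and oral CAI nesting in Protocol 21.3, the unflagged change of hypotony visit rule, and the wrong reference in SAP 8.3 and 8.3.1. The third needs correcting most, because literal use gives a wrong responder flag.

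The size is unknown. A reader might put several percentage points on it by adding assumed rates of office laser and brief hypotony. The documents give no such rates, and adding them would require every affected eye to be otherwise a success, with no overlap and nothing offsetting. The figures in the working show only how the rate responds to a given share of reclassified eyes.

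A reader might also conclude that scheduled visits should be the main hypotony rule. The documents do not settle this. Protocol 5.1 admits subjects after the Month 36 and 48 windows have passed, and those with only the Month 60 visit cannot meet a two-visit scheduled rule from extension data. The primary outcome, sight-threatening adverse events, is not affected.

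**What to change.** 1. In SAP 8.3 and 8.3.1, replace each reference to 8.1.4.3 as the failure definition with 8.1.5.
2. Reconcile Protocol 21.3 with Protocol 11.1 and 11.2 and SAP 8.1.5: remove the operating-room condition from the analysis definition and list oral CAI as its own item.
3. State which document's hypotony visit rule governs the success rate, note in the SAP any departure from Protocol 21.3, and report the other rule as a sensitivity row.

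The cost is wording in both documents and one extra row. A protocol change goes through the amendment process in Protocol 18.11. Either hypotony rule has a limitation to state beside the result: a scheduled-only rule cannot be met from extension visits by subjects with only Month 60, and the scheduled/unscheduled rule rests on discretionary visits in an open-label study.

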21.4 Interim Analyses

An annual interim analysis will be performed after the last subject completes his/her Month 36 and 48 Visit. The final analysis will be performed after the last subject completes his/her Month 60 Visit. Each interim analysis and final analysis will include the evaluation of safety and effectiveness of MicroShunt and Trabeculectomy as outlined above. All statistical analyses will be performed at the nominal 5% significant level without multiplicity adjustment.

22. Study Administration

22.1. Suspension or Early Termination

InnFocus reserves the right to terminate the study at any stage but intends to exercise this right only for valid scientific or administrative reasons, and reasons related to the protection of subjects.

Investigators, associated IRBs/IECs, and regulatory authorities, as applicable, will be notified in writing in the event of study termination.

Possible reasons for premature study termination include, but are not limited to, the following:

- The occurrence of unanticipated adverse events that present a significant or unreasonable risk to subjects enrolled in the study.
- An enrollment rate far below expectation that prejudices the conclusion of the study.
- A decision on the part of InnFocus to suspend or discontinue the surveillance of the product.

Both InnFocus and the Principal Investigator reserve the right to terminate the study according to the study contract and the requirements specified in ISO14155:2011 and relevant sections of Title 21 CFR Part 812. The Principal Investigator should notify the IRB/IEC in writing of the study's completion or early termination and send a copy of the notification to InnFocus.

22.1.1. Termination of Study Participation by the Investigator or Withdrawal of IRB/IEC Approval

Any Investigator in the study may discontinue participation in the study or withdraw approval of the study, respectively, with suitable written notice to InnFocus. Investigators, associated IRBs/IECs, and regulatory authorities, as applicable, will be notified in writing in the event of these occurrences.

In the event an IRB/IEC terminates an investigative site's participation in the study, participating Investigators, associated IRBs/IECs, and regulatory authorities, as applicable, will be notified in writing. Information on how enrolled subjects will be managed thereafter will be provided by InnFocus.

